8.3. Variables

There are two primary baseline periods of interest from which variables of interests will be evaluated: 1) 12-months fixed pre-index period and 2) a variable length baseline period is the maximal continuous enrollment window prior to index and at least 1-year pre-index. The primary post-index period is 12 months including the index date. Other observation periods are noted below.

Variable	Role	Data source(s)	Operational definition
Demographics (Table 1)		
Age	Baseline Characteristic	All	Age will be defined as of the index year.
Age groups	Baseline Characteristic	A11	Patients will be assigned to one of the following age groups based index age: 18–44, 45–64, and 65yo.
Gender	Baseline Characteristic	All	Gender will be captured from enrollment data.
Insurance type	Baseline Characteristic	All	Whether the patient was covered under a commercial or Medicare Supplemental (Truven DataType) insurance plan will be captured.
Plan type	Baseline Characteristic	All	HMO, EPO, GPO, etc via.
			PlanType.
Geographic region	Baseline Characteristic	All	The United States (U.S.) region in which the study patient is enrolled in a health plan will be determined and reported and states will be categorized into five geographic regions: Northeast, South, Midwest, West, Unknown (https://www2.census.gov/geo/pdfs/maps- data/maps/reference/us_regdiv.pdf).
Variable length baselin	eBaseline Characteristic	All	Identify the duration of variable length (ie, all available pre-index continuous enrollment) baseline period.

Variable	Role	Data source(s)	Operational definition
RA-Related Medication	Use in Pre-Index (Tabl	e 2)	
Pre-index biologic DMARD use	Baseline Characteristic	All	A count of unique (on different days) pharmacy/admin claims on different days for ADA/ETN will be created during the 12 month baseline period.
Time from last pre- index bDMARD to index	Baseline Characteristic	All	A variable for the interval between last ADA/ETN pharmacy/administration claim and index. Stratify by <3 mos, 3-<6 mos and 6-12 mos pre-index.
Time from first pre- index bDMARD to index	Baseline Characteristic		A variable for the interval between first ADA/ETN pharmacy/administration claim during the variable length baseline and index. Stratify by <6, 6-12, ≥12 mos.

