NB-DMARD use	Outcome	All	 For patients who initiate combination therapy, will look for select NBDMARD (MTX, SSZ, LEF, HCQ) discontinuation or switch from start of NB-DMARD through end of 12-month post-index period. Definitions of treatment patterns are similar to 5 persistent groups above for index advanced therapy medications and using a 60 day gap. A 28-day supply will be assumed for MTX administrations. For those who initiated advanced monotherapy, addition of one for four main or other NBDMARDs will be evaluated.

Variable	Role	Data source(s)	Operational definition
Medication Effectiveness Proxy Algorithm (Curtis et al) ¹⁴	Outcome	All	Medication effectiveness at one year after the index date will be determined using the following six criteria. For each of the 6 criteria, a 0/1 flag will be created. Patients who are effectively treated for each of the 6 criteria will be considered effectively treated. Patients who fail any of the 6 criteria are therefore not effectively treated.
			1.High adherence to index agent: For all medications, a proportion of days covered (PDC) will be calculated based on total days supply over the 1 year follow-up. The PDC will be calculated by using the date of service and the day supply for each fill of the index medication. Patients with early refills will be allowed to stockpile medications up to a maximum of 14 days total for later use. Patients with PDC ≥ 0.8 will be considered highly adherent and effectively treated. The original Curtis algorithm referenced an MPR;however, more recent studies are using PDCs or similarly described measure. ¹⁵

Variable	Role	Data source(s)	Operational definition
		I	2.No increase in dose (see below)
			for index medication compared to the
			starting dose. Dose escalation will be
			identified per the criteria listed
			below.
			ADA: At least 1 claim in the follow-up period with an average weekly dose of at least 40 mg/week. ETN: At least 1 claim in the follow-up period with an average weekly dose of at least 100 mg/week.
			TOFA: At least 1 claim in the
			follow-up period with an average
			weekly dose of at least 20 mg/day
			for IR and 22 mg/day for XR.
			for the and 22 mg/day for XR.
			3.No switching from the index medication to a different advanced therapy. A switch will be defined as use of a different bDMARD or JAKi any time during the follow-up period noting the availability of newer advanced therapies after original 2011 Curtis algorithm publication.

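### Effectiveness criterion 2 is defined as no dose increase from the starting dose, but its drug rules never use the starting dose, so a patient who starts and stays at the threshold fails without any increase

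*Combined protocol and SAP*

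**What the plan says.** Section 8.3 (Medication Effectiveness Proxy Algorithm, criterion 2) requires no rise in dose. The reference point and the method of identification run over three consecutive lines of the table: "for index medication compared to the" / "starting dose. Dose escalation will be" / "identified per the criteria listed" below.

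The listed rules are:

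- Adalimumab: "At least 1 claim in the follow-up period with an average weekly dose of at least 40 mg/week".
- Etanercept: "ETN: At least 1 claim in the follow-up period with an average weekly dose of at least 100 mg/week".
- Tofacitinib: one follow-up claim with an average "weekly dose of at least 20 mg/day" for the immediate-release form, or 22 mg/day for XR.

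None of the rules mentions the starting dose, and criterion 2 does not say whether the index claim is a follow-up claim. The general text of Section 8.3 says "The primary post-index period is 12 months including the index date". The consequence of failing is also explicit: "Patients who fail any of the 6 criteria are therefore not effectively treated".

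The composite is a secondary outcome (Section 7.2). It is summarised by cohort (Section 8.7.2.2) and is to be modelled by logistic regression (Section 8.7.6), although Section 8.7.4 lists it only as a possible multivariable outcome.

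**The concern.** The definition describes a change within a patient. The rules measure a level. The two agree only for patients who start below the level, and nothing in the inclusion criteria (Section 8.2.1) restricts the starting dose. A patient who starts at the level and stays there has no dose increase but meets the rule for escalation. Because one failed criterion decides the composite, that patient moves from effective to not effective on the strength of criterion 2 alone.

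The levels are drug-specific and the cycling comparisons are between drugs, so the share of patients caught in this way need not be the same in each cohort. The tofacitinib rule also attaches mg/day figures to an average weekly dose. That is a slip of wording, but a programmer needs it settled.

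**Working it through.** The plan gives no figure to reproduce here, so the check applies the rule to dose paths and then sizes the effect on stated assumptions.

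**Step 1: the rule on dose paths.** The threshold is from Section 8.3 (adalimumab, 40 mg/week); the paths are illustrative. The rule as written flags a patient if any follow-up dose is ≥ 40. The stated definition flags if any later dose exceeds the starting dose. The corrected rule flags if a later dose is ≥ 40 and exceeds the starting dose.

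| Start → later (mg/week) | As written, index claim counted | As written, index claim not counted | Stated definition | Corrected rule |
|---|---|---|---|---|
| 40 → 40 | flagged | flagged | no increase | not flagged |
| 40 → 20 | flagged | not flagged | no increase | not flagged |
| 20 → 20 | not flagged | not flagged | no increase | not flagged |
| 20 → 40 | flagged | flagged | increase | flagged |
| 20 → 30 | not flagged | not flagged | increase | not flagged |

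The first row is the main fault, and it does not depend on how the index claim is treated. The second row is a fault only if the index claim counts as follow-up. The last row is a rise below the threshold, which the corrected rule also leaves uncounted. With the index claim counted, the same pattern (stay at the threshold, halve from it, stay at half of it, rise from half to it, rise from half to 0.9 of it) gave the same results for etanercept at 100 mg/week and tofacitinib at 20 and 22 mg/day.

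**Step 2: size within one cohort.** The documents supply none of the inputs, so these are assumptions:

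- E, the share passing the other five criteria: 20% to 50%.
- s, the share of those failed on criterion 2 with no rise: 0% to 10%.

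Reported effective rate minus the rate under the corrected rule = −E × s.

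- s = 0: 0 points, whatever E is.
- E = 20%, s = 10%: −0.20 × 0.10 = −2.0 points.
- E = 40%, s = 5%: −0.40 × 0.05 = −2.0 points.
- E = 50%, s = 10%: −0.50 × 0.10 = −5.0 points.

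**Step 3: effect on a comparison.** For cohorts A and B, the difference in effective rates (A minus B) shifts by −(E_A × s_A) + (E_B × s_B). The shift is zero when the two products are equal. The documents give no basis for saying whether they are.

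**The case against.** The strongest defence is that the criterion should be read as a whole: the opening sentence sets the comparison with the starting dose, and the listed levels only say how large a rise must be to count. On that reading a 40 → 40 patient passes. A programmer might well code it so, and Section 8.8 provides for a programming plan and review by a second programmer. But the sentence hands identification of escalation to the listed rules, and those rules can be applied in full without knowing the starting dose. The reading is possible, but the text does not state it.

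A second defence is that usual starting doses lie below the listed levels. The documents state no usual starting dose and do not limit entry to one. If the defence is true, s is close to zero and the correction changes almost nothing.

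Third, the composite is a cited published algorithm. The protocol announces its departures for criteria 1, 3 and 4 but none for criterion 2, which is consistent with levels carried over from the source. That does not settle which of two conflicting statements governs. Section 8.9 acknowledges incomplete validation across the drugs, which is a different matter.

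Two parts of the case against stand. The size rests entirely on assumed inputs. And a reader might infer that the rule errs in both directions, because a 20 → 30 rise goes unflagged. That should not be counted as an error here: the listed levels can fairly be read as setting the size of rise that matters, and the correction keeps them. The loss is therefore 0 to 5 points in one direction, not a symmetric range.

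**Conclusion.** The rule is wrong as written, and the severity is minor. A patient who starts and stays at the listed level is classed as escalated, and so as not effectively treated, with no increase in dose. If the index claim counts as follow-up, which the general text of Section 8.3 implies but criterion 2 does not say, a patient who starts at the level and then reduces is flagged too.

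The effect is to lower a cohort's effective rate by E × s: 0 to 5 points on the assumed ranges. The textual fault is certain; its practical size is unknown and may be small.

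A reader might also infer that the comparison of cohorts is biased, or that it favours a particular drug. The documents do not support this, because they give no cohort-specific share of patients starting at the level. Nor is the primary outcome touched: persistence is defined from gaps and switches, not from dose.

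**What to change.** Redefine escalation in criterion 2 as at least one claim after the index claim whose average dose is at or above the listed level **and** above that patient's index-claim dose. State that rises staying below the level are not counted. Express the tofacitinib levels as average daily dose.

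The comparator is already available: Section 8.2.1 requires every cohort to be new to its index drug, so the starting dose is the dose on the index claim. The cost is a reworded criterion and a few lines of code, with no new data.

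Three additions are optional:

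- A tolerance, so that recording differences are not read as increases. The same 160 mg adalimumab fill is 160 × 7/30 = 37.3 mg/week over 30 days and 160 × 7/28 = 40.0 over 28 days, a difference of 30/28 − 1 = 7.1%. A move from 20 mg/day immediate-release to 22 mg/day XR is 22/20 − 1 = 10.0%. Criterion 5b already uses a 20% margin for glucocorticoids. The price is that a rise within the margin that crosses the level would not count.
- A count, by cohort, of patients whose index claim is already at or above the level. This would bound s directly.
- The fixed-level flag kept as a sensitivity analysis.

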Comorbidities of interest	Baseline Characteristic	All	 0/1 flags will be created to identify the presence of the following comorbidities during the 12-month baseline period (see Appendix 4). Cardiovascular diseases. Chronic obstructive pulmonary disease (COPD). Asthma. Kidney disease. Diabetes. Depression. Anxiety. Liver disease. Sleep disorders. Hypertension. Hyperlipidemia. Interstitial lung disease.

Variable	Role	Data source(s)	Operational definition
Cumulative OOP Costs pre-index	Baseline Characteristic	All	The total, pharmacy and medical OOP costs (deductible+copay+coinsurance) resource use from January 1 of index year through Index.
Index Date OOP costs	Baseline Characteristic	All	Total, pharmacy (excluding index medication) and medical OOP costs on index date.
Index Medication (Table	4)		
Index Prescriber	Baseline Characteristic	All	Top 5 index medication prescriber specialties and other or unknown will be identified.
Index month/year	Baseline Characteristic	All	The month and year of the patient's index date (start of TOFA, ETN, ADA) will be identified.
Index Medication OOP costs	Baseline Characteristic	All	The index medication pharmacy OOP costs (deductible+copay+coinsurance) will be identified for the first index medication rx and cumulative by month (1-12) of follow-up (only looking at pharmacy claims here noting index event is a prescription fill).
Index combination vs. monotherapy regimen status	Baseline Characteristic	All	Patients with a use of one of the 4 main NB- DMARDs (injectable and oral MTX, SSZ, HCQ, LEF) within 90 days on or after the index date will be considered as being treated with combination therapy regimen, others will be classified as monotherapy. For monotherapy, will evaluate 6-mos pre-index use of each of the four main and other NB- DMARDs. For combination regiment, will stratify by 6 mos pre-index use of the four main and other NB-DMARDs.
Post-Index Treatment Pa	tterns (Table 4)		
Treatment Persistence (5 groups)	Outcome	All	Persistent with the index medication will be defined as not having a gap in therapy of at least 60 days between fills/admins. For retail pharmacy (rx) claims the day supply will be utilized and rounded to the nearest 28-day supply for ETN and ADA and 30- day supply for TOFA. For subcutaneous ETN and ADA administrations, a 28-day supply will be assumed.

Variable	Role	Data source(s)	Operational definition

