			4.No adding of a new non-biologic DMARD to the index therapy.
			Measure has been modified to
			distinguish outcomes for advanced
			monotherapy vs. NB-DMARD
			comobination regiments, noting
			patients may not have NB-DMARD in
			6-mos pre-indes but start a
			combination regimen. For those
			starting a monotherapy index
			medication regimen, the initiation of a
			select NB-DMARD will be identified
			in the follow up period as addition of
			NB-DMARD. For those starting a
			combination index medication
			regimen, presence of a different NB-
			DMARD in follow-up will be flagged
			as failing the algorithm.

Variable	Role	Data source(s)	Operational definition
			5. Oral glucocorticoids. Only National Drug Code (NDC) codes for oral glucocorticoids will be included.
			5a. For patients with no claims for oral glucocorticoid prescriptions in the six months prior to the index date: cannot receive more than 30 days of oral glucocorticoids between (index date + 89) to (index date + 359). 30 days of oral glucocorticoids will be determined by summing up the day supply of all glucocorticoids claims with a fill date between (index date + 89) to (index date + 359).
			5b. For patients with claims for oral glucocorticoids during the six months prior to the index date: No increase in oral glucocorticoid dose ≥20% during months 6- 12 after index compared to the 6 months before the index date. Increase in oral glucocorticoids will be determined from the prednisone equivalent dose for all glucocorticoid claims filled during the respective time periods.
			6. At most one parenteral or intra- articular glucocorticoid joint injection on unique days after the patient had been on biologic treatment for more than three months between (index date + 89) to (index date + 359). CPT codes 20600, 20605, 20610.
Change in Resource Use RA-related healthcare	and Costs (Tables 5 an Outcome	all	The number of patients with and number of encounters
resource use		- 141	(including zeros) for each RA- related medical and pharmacy resource use will be evaluated in the 12-month pre- and post-index periods. See Section 8.3.1 for details on calculating cost and healthcare utilization.
All-cause healthcare resource use	Outcome	All	The number of patients with and number of claims (including zeros) for each all-cause medical and pharmacy resource use will be evaluated in the 12-month pre- and post-index periods. See Section 8.3.1 for details on calculating cost and healthcare utilization.

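### Effectiveness criterion 4 tests for presence of a different NB-DMARD without checking pre-index use, so some patients on unchanged background therapy are scored as not effectively treated

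*Combined protocol and SAP*

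**What the plan says.** The Medication Effectiveness Proxy row in Section 8.3 heads its fourth criterion "4.No adding of a new non-biologic DMARD to the index therapy". Two branches then define failure. For a monotherapy index "medication regimen, the initiation of a" select NB-DMARD during follow-up counts as an addition. For a combination index "regimen, presence of a different NB"-DMARD during follow-up fails the patient. The criterion mentions pre-index use only to explain why the published algorithm was modified: "patients may not have NB-DMARD in" the six months before index and yet start a combination regimen.

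The branch is decided by the index regimen row of the same section. It begins "Patients with a use of one of the 4 main NB- DMARDs (injectable and oral MTX, SSZ, HCQ, LEF", and such use "within 90 days on or after the index date will be considered as being treated with combination therapy regimen"; everyone else is monotherapy. That row also collects six-month pre-index use of the main and other NB-DMARDs for monotherapy patients. For combination patients it "will stratify by 6 mos pre-index use of the four main and other NB-DMARDs". Criterion 4 does not draw on either.

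Failing any one of the six criteria makes a patient not effectively treated. The proxy is a secondary outcome (Section 7.2) and is modelled by logistic regression (Section 8.7.6).

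**The concern.** The heading asks whether something was added. The combination branch asks whether something is there. These differ for any patient already taking a second NB-DMARD before index, and the rule has no look-back to separate them. The set of drugs that can define the regimen (four) is also narrower than the set that can, read literally, trigger failure (any NB-DMARD, including the *other* medications in Appendix 2).

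If an unchanged drug triggers failure, stable background therapy is read as lack of effect of the index agent. The error follows background NB-DMARD use. If that use differs between tofacitinib switchers and TNFi cyclers, or between out-of-pocket cost groups, the effectiveness comparison could be shifted as well as blurred. Covariate adjustment does not repair a misclassified outcome, and Section 8.9 does not list this among the limitations.

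**Working it through.** The plan gives no figure to reproduce: Section 8.5 reports no sample size computation, and no rate of NB-DMARD use is stated. The check applies the written rule to patients whose background therapy does not change.

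**Inputs (Section 8.3 unless noted).** Main drugs: methotrexate (MTX), sulfasalazine, hydroxychloroquine (HCQ), leflunomide. Regimen window: 90 days on or after index. *Select* NB-DMARD: the same four drugs, from the NB-DMARD use row. Gap that counts as NB-DMARD discontinuation: 60 days. Azathioprine is listed under *other* medications in Appendix 2.

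**Step 1: apply the rule.**

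| Unchanged therapy | Label | Criterion 4 |
|---|---|---|
| One main drug, monthly fills | Combination | Passes |
| MTX plus azathioprine | Combination | Fails as written: azathioprine cannot define the regimen but is a different NB-DMARD |
| MTX plus HCQ, both filled within 90 days | Combination | Passes if *different* is read against all main drugs in the window; fails if read against one qualifying drug |
| MTX monthly, HCQ refilled on day 95 | Combination | Fails if *use* means a fill |
| Azathioprine only | Monotherapy | Passes, because *select* means the four main drugs |
| One main drug on 90-day fills, first refill after the window | Monotherapy if *use* means a fill | Fails only if *initiation* also means the first follow-up claim |

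The second and fifth rows show the inconsistency between branches: the same unchanged azathioprine fails a combination patient and passes a monotherapy patient.

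**Step 2: how often a late refill could miss the window, if *use* means a fill.** Let S be days supplied, d the days from the last pre-index fill to index (1 to S), and g the uncovered days before the refill (0 to 59, below the discontinuation gap). The next fill falls on day S − d + g. It misses the window if that exceeds 90, or 89 if the index date is counted as the first of the 90 days.

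- 28-day supply: latest possible day 28 − 1 + 59 = 86. None miss.
- 30-day supply: 30 − 1 + 59 = 88. None miss.
- 90-day supply, g = 0: latest day 89. None miss.
- 90-day supply, g = 7: day 97 − d, missed for d = 1–6 or 1–7, so 6/90 to 7/90 = 6.7% to 7.8%.
- 90-day supply, g = 14: 13/90 to 14/90 = 14.4% to 15.6%.
- 90-day supply, g = 30: 29/90 to 30/90 = 32.2% to 33.3%.

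These percentages assume d is uniform over 1 to 90. They are shares of continuing 90-day fillers with that gap, not shares of a cohort.

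**Step 3: effect on the proxy.** If a fraction c of a cohort is falsely failed on criterion 4, and a fraction e of those would otherwise pass all six criteria, the proportion effectively treated is understated by c × e. Neither is in the documents. Purely for scale, with e = 0.30: c = 0.03 gives 0.03 × 0.30 = 0.9 percentage points, and c = 0.10 gives 0.10 × 0.30 = 3.0 points.

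**Step 4: is a six-month look-back long enough?** With a supply of up to 90 days and a gap below 60 days, a continuing user's last pre-index fill is at most 90 + 59 = 149 days before index, inside roughly 180 days.

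**The case against.** The strongest reply is that the move from a pre-index reference to an index-regimen reference is deliberate and explained, and that the ordinary continuing user is handled correctly. Both statements are true. A reader might infer that anyone who simply stays on a long-standing NB-DMARD is scored as a failure. The documents do not support that: one main drug refilled within 90 days puts the patient in the combination group, where that drug is not a different one, and an *other* drug taken alone does not fail a monotherapy patient.

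A reader might also infer that late refills in the monotherapy branch are miscounted as additions. The text does not settle this. The regimen row speaks of *use*, not of a fill, and supply dispensed the day before index could count as use in the window. Under a heading about new drugs, *initiation* can fairly be read as excluding a refill. Both terms must be read the other way for the error to occur, and Step 2 shows it would then be confined to longer supplies.

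It can further be said that *different NB-DMARD* was meant to cover only the four *select* drugs named for the monotherapy branch. That is possible, but the combination branch does not say so. The declared reason for the modification concerns patients with no pre-index NB-DMARD who start a combination. It gives no reason to fail patients who continue one.

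**Conclusion.** The point stands in a limited form. As written, the combination branch fails a patient who continues a main NB-DMARD together with a long-standing Appendix 2 *other* drug, although nothing was added. A continued second main drug is also failed if *different* is read against a single drug or if its fill falls outside the window. The monotherapy error is conditional on the two readings named above.

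Within a cohort, this error can only lower the proportion effectively treated. Its size cannot be computed, because the documents give neither the frequency of these regimens nor the pass rate on the other criteria. It would be tempting to quote a between-cohort bias: the Step 3 values, with 10% affected in one arm and 3% in the other, differ by 3.0 − 0.9 = 2.1 points. That figure comes entirely from the chosen imbalance; nothing in the documents says that the cohorts differ, or in which direction. A link between out-of-pocket group and 90-day fills is likewise conjecture.

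Only the secondary effectiveness proxy is affected. Persistence duration, the primary outcome, does not use criterion 4. The opposite error, in which a truly new main drug first filled on day 60 becomes part of the regimen and is not counted as an addition, is a separate consequence of the sponsor's modification.

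**What to change.** In both branches of criterion 4, count an NB-DMARD as new only if it is neither part of the index regimen nor on any pharmacy or administration claim in the six months before index, whether a main or an *other* drug. This retains the sponsor's modification, because a drug started with the index regimen still does not count as a failure. It also matches criterion 5, which already conditions on six-month pre-index glucocorticoid claims.

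State as well whether *select* and *different NB-DMARD* cover the four main drugs or all of Appendix 2, and reconcile this with the NB-DMARD use row, which evaluates additions of main or other drugs for monotherapy starters.

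The cost is a small programming change on variables that the index regimen row already requires. The downside is that re-adding a drug stopped within the previous six months would no longer count as a failure.
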